#### • Other situations:

- Medical or scientific judgment should be exercised by the investigator in deciding whether SAE reporting is appropriate in other situations such as important medical events that may not be immediately life-threatening or result in death or hospitalization but may jeopardize the participant or may require medical or surgical intervention to prevent one of the other outcomes listed in the above definition. These events should usually be considered serious.
- o Examples of such events include invasive or malignant cancers, intensive treatment in an emergency room or at home for allergic bronchospasm, blood

dyscrasias or convulsions that do not result in hospitalization, or development of drug dependency or drug abuse.

# **10.3.3.** Definition of Product Complaints

# **Product complaint**

- A PC is any written, electronic, or oral communication that alleges deficiencies related to the identity, quality, durability, reliability, safety, effectiveness or performance of a study intervention. When the ability to use the study intervention safely is impacted, the following are also PCs:
  - o deficiencies in labeling information, and
  - use errors for device or drug-device combination products due to ergonomic design elements of the product.
- PCs related to study interventions used in clinical trials are collected to ensure the safety
  of participants, monitor quality, and to facilitate process and product improvements.
- Investigators will instruct participants to contact the site as soon as possible if he or she has a PC or problem with the study intervention so that the situation can be assessed.
- An event may meet the definition of both a PC and an AE/SAE. In such cases, it should be reported as both a PC and as an AE/SAE.

# 10.3.4. Recording and Follow-Up of AE and/or SAE and Product Complaints AE, SAE, and PC recording

- When an AE/SAE/PC occurs, it is the responsibility of the investigator to review all
  documentation (for example, hospital progress notes, laboratory reports, and diagnostics
  reports) related to the event.
- The investigator will then record all relevant AE/SAE/PC information in the participant's medical records, in accordance with the investigator's normal clinical practice. AE/SAE information is reported on the appropriate CRF page and PC information is reported on the Product Complaint Form.
- Note: An event may meet the definition of both a PC and an AE/SAE. In such cases, it should be reported as both a PC and as an AE/SAE.
- It is **not** acceptable for the investigator to send photocopies of the participant's medical records to sponsor or designee in lieu of completion of the CRF page for AE/SAE and the Product Complaint Form for PCs.
- There may be instances when copies of medical records for certain cases are requested by sponsor or designee. In this case, all participant identifiers, with the exception of the participant number, will be redacted on the copies of the medical records before submission to sponsor or designee.
- The investigator will attempt to establish a diagnosis of the event based on signs, symptoms, and/or other clinical information. Whenever possible, the diagnosis (not the individual signs/symptoms) will be documented as the AE/SAE.

# **Assessment of intensity**

The investigator will make an assessment of intensity for each AE and SAE reported during the study and assign it to one of the following categories:

- Mild: A type of AE that is usually transient and may require only minimal treatment or therapeutic intervention. The event does not generally interfere with usual activities of daily living.
- Moderate: A type of AE that is usually alleviated with additional specific therapeutic intervention. The event interferes with usual activities of daily living, causing discomfort but poses no significant or permanent risk of harm to the research participant.
- Severe: A type of AE that interrupts usual activities of daily living, or significantly affects clinical status, or may require intensive therapeutic intervention. An AE that is assessed as severe should not be confused with a SAE. Severe is a category utilized for rating the intensity of an event; and both AEs and SAEs can be assessed as severe.

An event is defined as "serious" when it meets at least one of the predefined outcomes as described in the definition of an SAE, NOT when it is rated as severe.

# **Assessment of causality**

- The investigator is obligated to assess the relationship between study intervention and each occurrence of each AE/SAE. The investigator will use clinical judgment to determine the relationship.
- A "reasonable possibility" of a relationship conveys that there are facts, evidence, and/or arguments to suggest a causal relationship, rather than a relationship cannot be ruled out.
- Alternative causes, such as underlying disease(s), concomitant therapy, and other risk factors, as well as the temporal relationship of the event to study intervention administration will be considered and investigated.
- The investigator will also consult the IB in their assessment.
- For each AE/SAE, the investigator **must** document in the medical notes that he/she has reviewed the AE/SAE and has provided an assessment of causality.
- There may be situations in which an SAE has occurred and the investigator has minimal information to include in the initial report to sponsor or designee. However, it is very important that the investigator always make an assessment of causality for every event before the initial transmission of the SAE data to sponsor or designee.
- The investigator may change their opinion of causality in light of follow-up information and send a SAE follow-up report with the updated causality assessment.
- The causality assessment is one of the criteria used when determining regulatory reporting requirements.

# Follow-up of AEs and SAEs

• The investigator is obligated to perform or arrange for the conduct of supplemental measurements and/or evaluations as medically indicated or as requested by sponsor or designee to elucidate the nature and/or causality of the AE or SAE as fully as possible. This may include additional laboratory tests or investigations, histopathological examinations, or consultation with other health care professionals.

• If a participant dies during participation in the study or during a recognized follow-up period, the investigator will provide sponsor or designee with a copy of any postmortem findings including histopathology.

# 10.3.5. Reporting of SAEs

# SAE reporting via an electronic data collection tool

- The primary mechanism for reporting an SAE will be the electronic data collection tool.
- If the electronic system is unavailable, then the site will use the SAE paper form (see next section) to report the event within 24 hours.
- The site will enter the SAE data into the electronic system as soon as it becomes available.
- After the study is completed at a given site, the electronic data collection tool will be taken off-line to prevent the entry of new data or changes to existing data.
- If a site receives a report of a new SAE from a study participant or receives updated data on a previously reported SAE after the electronic data collection tool has been taken off-line, then the site can report this information on a SAE paper form (see next section) or to the sponsor or designee by telephone.
- Contacts for SAE reporting can be found in the Global Patient Safety Clinical Trial SAE Transmission Cover Sheet and Form.

#### SAE reporting via paper form

- Facsimile transmission of the SAE paper form is the preferred method to transmit this information to the sponsor or designee.
- Initial notification via telephone does not replace the need for the investigator to complete and sign the SAE CRF pages within the designated reporting time frames.
- Contacts for SAE reporting can be found in the Global Patient Safety Clinical Trial SAE Transmission Cover Sheet and Form.

# 10.3.6. Regulatory Reporting Requirements

#### **SAE** regulatory reporting

Prompt notification by the investigator to the sponsor of a SAE is essential so that legal obligations and ethical responsibilities toward the safety of participants and the safety of a study intervention under clinical investigation are met.

• The sponsor has a legal responsibility to notify both the local regulatory authority and other regulatory agencies about the safety of a study intervention under clinical investigation. The sponsor will evaluate the reported SAEs, including confirmation of relatedness and assessment of expectedness. The sponsor has processes for safety reports for identification, recording, and expedited reporting of SUSARs according to local regulatory requirements. The sponsor will comply with country-specific regulatory requirements relating to safety reporting to the regulatory authority, IRB/IEC, and investigators.

• An investigator who receives an investigator safety report describing a SAE or other specific safety information (for example, summary or listing of SAEs) from the sponsor will review and then file it along with the IB and will notify the IRB/IEC, if appropriate according to local requirements.

# 10.4. Appendix 4: Contraceptive and Barrier Guidance

# 10.4.1. Definitions

Word/Phrase	Definition	
Women of childbearing potential (WOCBP)	Adult females are considered WOCBP unless they are WNOCBP.	
Women not of childbearing potential (WNOCBP)	
 
Females are considered WNOCBP if they
 
have a congenital anomaly such as Müllerian agenesis, resulting in confirmed infertility
 
are infertile due to surgical sterilization, or
 
are menopausal.
 
Acceptable surgical sterilization methods are hysterectomy, bilateral salpingo-oophorectomy, bilateral salpingectomy, or bilateral oophorectomy.
 
	
Menopausal state	oophorectomy.  The menopausal state is defined as a woman:  • at any age at least 6 weeks post-surgical bilateral oophorectomy with or without hysterectomy, confirmed by operative note; or  • aged at least 40 years and up to 55 years with an intact uterus, not on hormone therapy³, who has had cessation of menses for at least 12 consecutive months without an alternative medical cause, AND with a follicle-stimulating hormone ≥40 mIU/mL; or  • 55 years or older not on hormone therapy, who has had at least 12 months of spontaneous amenorrhea, or  • aged at least 55 years with a diagnosis of menopause prior to starting hormone replacement therapy.  a Women should not be taking medications during amenorrhea such as oral contraceptives, hormone replacement therapy (HRT), gonadotropin-releasing hormone, anti-estrogens, selective estrogen receptor modulators, or chemotherapy that could induce transient amenorrhea. Women on HRT and those whose menopausal status cannot be confirmed will be required to comply with the protocol contraception requirements if they wish to continue HRT during the study. Otherwise, they must discontinue	

# 10.4.2. Contraception Guidance

## **Contraception guidance for Females**

WOCBP who are completely abstinent as their preferred and usual lifestyle, or exclusively engage in a same-sex relationship as their preferred and usual lifestyle must follow the rules in this table.

Must	Must not
agree to either remain abstinent or exclusively engage in same-sex relationship, and not plan a pregnancy during the study	
 
use periodic abstinence methods         
 
calendar
 
ovulation
 
symptothermal, or
 
post-ovulation
 
 
 
declare abstinence just for the duration of a trial, or
 
use the withdrawal method
 

WOCBP who are NOT completely abstinent as their preferred and usual lifestyle, or who do NOT exclusively engage in same-sex relationship as their preferred and usual lifestyle, must follow the rules in this table.

#### Must..

Agree to use 1 highly effective method of contraception, or a combination of 2 effective methods of contraception.

These methods of contraception must be used for the duration of the study.

#### Contraception guidance for all male participants

For males, no contraception is required except in compliance with specific local government study requirements.

# **Examples of different methods of contraception**

Methods	Examples
Highly effective contraception (less than 1% failure rate)	
 
fallopian tubal sterilization methods other than bilateral salpingectomy (laparoscopic bipolar electrocoagulation, plastic ring application on the uterine tubes, fallopian tube ligation, hysteroscopic sterilization).         Note: Bilateral salpingectomy is indicative of permanent sterilization.         Please see the WNOCBP definition above.     
 
combination oral contraceptive pill
 

 
progestin-only contraceptive pill (minipill)
 
implanted contraceptives
 
injectable contraceptives
 
contraceptive patch (only women <198 pounds or 90 kg)
 
total abstinence
 
vasectomy - for males in clinical trials and for female partner (if only sexual partner)
 
fallopian tube implants (if confirmed by hysterosalpingogram)
 
vaginal ring containing combination hormone medication, or
 
intrauterine devices
 
penile condom with spermicide
 
vaginal condom with spermicide
 
cervical sponge with spermicide, or
 
cervical cap with spermicide
 
Note: Penile and vaginal condoms should not be used in combination.
 

 
spermicide alone
 
periodic abstinence
 
fertility awareness (calendar method, temperature method, cervical mucus, or symptothermal)
 
withdrawal
 
post coital douche, or
 

# 10.6. Appendix 6: Liver Safety: Suggested Actions and Follow-up Assessments

# Hepatic evaluation testing

See Section 8.2.11 for guidance on appropriate test selection.

The Lilly-designated central laboratory should complete the analysis of all selected testing except for testing listed in the investigator-designated local laboratory table. The central laboratory will report results if a validated test or calculation is available.

Local testing may be performed *in addition to central testing* when necessary for immediate participant management.

The local laboratory must be qualified in accordance with applicable local regulations.

Tests assayed by Lilly-designated central laboratory		
Hepatic Hematology Panel	Hepatitis A virus (HAV) testing:	
Hemoglobin	HAV total antibody	
Hematocrit	HAV IgM antibody	
Erythrocytes (RBCs - red blood cells)	Hepatitis B virus (HBV) testing:	
Leukocytes (WBCs - white blood cells)	Hepatitis B surface antigen (HBsAg)	
Differential:	Hepatitis B surface antibody (anti-HBs)	
Neutrophils, segmented	Hepatitis B core total antibody (anti-HBc)	
Lymphocytes	Hepatitis B core IgM antibody	
Monocytes	HBV DNAb	
Basophils	Hepatitis C virus (HCV) testing:	
Eosinophils	HCV antibody	
Platelets	HCV RNAb	
Cell morphology (RBC and WBC)	Hepatitis D virus (HDV) testing:	
Hepatic Clinical Chemistry Panel	HDV antibody	
Total bilirubin	HDV IgM antibody	
Direct bilirubin	Hepatitis E virus (HEV) testing:	
Alkaline phosphatase (ALP)	HEV IgG antibody	
Alanine aminotransferase (ALT)	HEV IgM antibody	
Aspartate aminotransferase (AST)	HEV RNAb	
Gamma-glutamyl transferase (GGT)	Anti-nuclear antibody (ANA)	
Creatine kinase (CK)	Anti-smooth muscle antibody (ASMA) a	
Hepatic Coagulation Panel	Anti-actin antibody c	
Prothrombin time, INR (PT-INR)	Immunoglobulin IgA (quantitative)	
Urine Chemistry	Immunoglobulin IgG (quantitative)	
Drug screen	Immunoglobulin IgM (quantitative)	
Haptoglobin		

Tests assayed ONLY by investigator-designated local laboratory		
Acetaminophen	Cytomegalovirus (CMV) testing:	
Acetaminophen protein adducts	CMV antibody	
Alkaline phosphatase isoenzymes	CMV DNAb	
Ceruloplasmin	Herpes simplex virus (HSV) testing:	
Copper	HSV (Type 1 and 2) antibody	
Ethyl alcohol (EtOH)	HSV (Type 1 and 2) DNA b	
Phosphatidylethanol (PEth)	Liver kidney microsomal type 1 (LKM-1) antibody	
Urine Chemistry	Microbiology Culture:	
Ethyl glucuronide (EtG)	Blood	
Epstein-Barr virus (EBV) testing:	Urine	
EBV antibody		
EBV DNAb		

a Not required if anti-actin antibody is tested.

b Reflex/confirmation dependent on regulatory requirements, testing availability, or both.

Not required if anti-smooth muscle antibody (ASMA) is tested.

# 10.7. Appendix 7: Tuberculosis Testing

This table describes recommendations for performing and interpreting TB tests. It also provides recommendations on TB retesting.

		<del>-</del>	
TB test type	How to perform the test	How to interpret the test	When to retest
PPD TST	
 
Inject 0.1 mL of tuberculin PPD into the inner surface of the forearm.
 
Notes:         
 
The injection should be made with a tuberculin syringe.
 
The TST is an intradermal injection. When placed correctly, the injection should produce a pale elevation of the skin (a wheal) 6 to 10 mm in diameter.
 
 
 
Measure induration at the site of intradermal injection from 48 to 72 hours after intradermal injection.         
 
Notes:
 
Test must be read during this window of time. Test does not need to be read at the study site but must be read by a trained medical professional, and the result must be provided to the study site before randomization.
 
The reaction should be measured in millimeters of induration (palpable, raised, hardened area, or swelling). The reader should not measure erythema (redness). The diameter of the indurated area should be measured across the forearm (perpendicular to the long axis).
 
 
 
	
 
An induration of 5 or more mm is considered positive in persons with:         
 
HIV infection
 
a recent contact with a person with TB disease
 
fibrotic changes on chest radiograph consistent with prior TB
 
organ transplants, or
 
immunosuppression for other reasons (for example, taking the equivalent of >15 mg per day of prednisone for 1 month or longer, or taking TNF alpha antagonists).
 
 
 
An induration of 10 or more mm is considered positive in all other potential clinical trial participants.
 
	Two-step testing (that is, repeat TST from 1 to 3 weeks after the first TST) is recommended for certain participant groups, including those:  receiving immunosuppressant treatment  having a history of temporally remote increased risk of TB infection, or  for whom the first test is negative, and retesting is recommended per local public health and/or professional medical society recommendations.

TB test type	How to perform the test	How to interpret the test	When to retest
IGRA for	Ensure that specimen handling, transport,	Results are provided by the laboratory	The investigator may discuss retesting
M tuberculosis	timing, and laboratory procedures meet all	assaying the test.	with the sponsor's designated medical
	requirements per package insert.		monitor if:
			• the investigator suspects a false
			positive IGRA result in a participant
			with no increased risk of TB infection
			during lifetime, and
			• there is no evidence of prior or current
			TB on physical examination and/or on
			CXR interpreted by radiologist and/or
			pulmonologist (investigator assessment
			by history and physical examination,
			and with documented CXR report).

Abbreviations: CXR = chest x-ray; IGRA = interferon gamma release assay; PPD = purified protein derivative; TNF = tumor necrosis factor; TST = tuberculin skin test.

# 10.8. Appendix 8: Examples of Infections That May Be Considered Opportunistic

For this study, infections are defined as opportunistic according to a consensus recommendation for clinical and postmarketing settings (Winthrop et al. 2015) with the following modifications:

- Candidiasis infections involving only the oral cavity or pharynx are not considered opportunistic. For an infection involving the oral cavity or pharynx to meet criteria for classification as an opportunistic infection, diagnostic evidence must confirm infection of the esophagus or gastrointestinal tract below the esophagus.
- Localized herpes zoster infections are not considered opportunistic. Only multidermatomal infections, disseminated infections, or a combination of these are considered opportunistic.
  - Localized or nonmultidermatomal are defined as involvement of the primary and/or adjacent dermatomes only. These may be complicated or uncomplicated:
    - Complicated: documented ocular (cornea or deeper structure; for example, iritis, keratitis, retinitis, and so on) or motor nerve involvement (for example, palsy). Postherpetic neuralgia does not meet criteria for motor nerve involvement.
    - Uncomplicated: localized or nonmultidermatomal cases that are not complicated.
  - Multidermatomal is defined as involvement beyond primary and adjacent dermatomes (that is, 4 or more contiguous dermatomes) or involvement of 2 or more noncontiguous dermatomes. These may be complicated or uncomplicated.
    - Complicated: documented ocular (cornea or deeper structure; for example, iritis, keratitis, retinitis, and so on) or motor nerve involvement.
    - Uncomplicated: multidermatomal cases.
  - Disseminated: systemic infection, visceral, or widespread cutaneous (for example, 5 or more dermatomes or from 3 to 4 dermatomes including at least 1 noncontiguous [nonadjacent]).
- Treatment-emergent, active tuberculosis infection is an opportunistic infection.

The tables in this appendix list examples of infections that may be considered opportunistic. These tables are intended to aid the investigator in recognizing infections which may be considered opportunistic. The lists are not exhaustive. For data analysis, infections will be categorized by Lilly as opportunistic according to the article by Winthrop et al. (2015).

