#### Infections and infectious disease

[16] Have a current or recent acute, active infection.

For at least 30 days before screening and up to the randomization/baseline visit, participants must have no symptoms or signs of confirmed or suspected infection, and must have completed any appropriate anti-infective treatment.

Note: Participants who have an upper respiratory infection or a vaginal candida infection who are being treated only symptomatically and not requiring systemic anti-infectives may be considered for enrollment if other study eligibility criteria are met. Enrollment of participants with other uncomplicated local infections should be discussed with the sponsor's designated medical monitor.

- [17] Have had any of these types of infections within 3 months prior to screening and up to randomization/baseline visit
  - Serious: requiring hospitalization, or intravenous or equivalent oral antibiotic treatment
  - Opportunistic: as defined in Winthrop et al. 2015 (see Appendix 8, Section 10.8)
  - Chronic: duration of symptoms, signs or treatment of 6 weeks or longer
  - Recurring: including, but not limited to herpes simplex, herpes zoster, recurring cellulitis, chronic osteomyelitis
    - Herpes zoster is considered active and ongoing until all vesicles are dry and crusted over
    - Participants with only recurrent, mild and uncomplicated orolabial herpes, or genital herpes, or both, may be discussed with the sponsor's designated medical monitor and may be considered for enrollment if other eligibility criteria are met.
- [18] Have HIV infection.
- [19] Have a current infection with HBV; that is, positive for HBsAg and/or PCR positive for HBV DNA (see Section 8.2.9).
- [20] Have a current infection with HCV; that is, positive for HCV RNA (see Section 8.2.10).
- [21] Have active TB (see Section 8.2.8).
- [22] Have or have had **CC** that has not been treated with a complete course of appropriate therapy as defined by the World Health Organization (WHO) or the United States Centers for Disease Control and Prevention (CDC), unless such treatment is underway (see Section 8.2.8).

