Cytomegalovirus disease Hepatitis B virus reactivation Hepatitis C virus progression Herpes simplex (invasive disease only) Herpes zoster (any form) Post-transplant lymphoproliferative disorder (Epstein-Barr virus) Progressive multifocal leukoencephalopathy (PML), John Cunningham (JC) virus  Fungal Aspergillosis (invasive disease only) Blastomycosis Candidiasis (invasive disease or oropharyngeal, esophageal. Not isolated lingual) Coccidioidomycosis Cryptococcosis
Hepatitis B virus reactivation Hepatitis C virus progression Herpes simplex (invasive disease only) Herpes zoster (any form) Post-transplant lymphoproliferative disorder (Epstein-Barr virus) Progressive multifocal leukoencephalopathy (PML), John Cunningham (JC) virus  Fungal Aspergillosis (invasive disease only) Blastomycosis Candidiasis (invasive disease or oropharyngeal, esophageal. Not isolated lingual) Coccidioidomycosis Cryptococcosis
Hepatitis C virus progression  Herpes simplex (invasive disease only)  Herpes zoster (any form)  Post-transplant lymphoproliferative disorder (Epstein-Barr virus)  Progressive multifocal leukoencephalopathy (PML), John Cunningham (JC) virus  Fungal  Aspergillosis (invasive disease only)  Blastomycosis  Candidiasis (invasive disease or oropharyngeal, esophageal. Not isolated lingual)  Coccidioidomycosis  Cryptococcosis
Herpes simplex (invasive disease only) Herpes zoster (any form) Post-transplant lymphoproliferative disorder (Epstein-Barr virus) Progressive multifocal leukoencephalopathy (PML), John Cunningham (JC) virus  Fungal Aspergillosis (invasive disease only) Blastomycosis Candidiasis (invasive disease or oropharyngeal, esophageal. Not isolated lingual) Coccidioidomycosis Cryptococcosis
Herpes zoster (any form) Post-transplant lymphoproliferative disorder (Epstein-Barr virus) Progressive multifocal leukoencephalopathy (PML), John Cunningham (JC) virus  Fungal Aspergillosis (invasive disease only) Blastomycosis Candidiasis (invasive disease or oropharyngeal, esophageal. Not isolated lingual) Coccidioidomycosis Cryptococcosis
Post-transplant lymphoproliferative disorder (Epstein-Barr virus) Progressive multifocal leukoencephalopathy (PML), John Cunningham (JC) virus  Fungal Aspergillosis (invasive disease only) Blastomycosis Candidiasis (invasive disease or oropharyngeal, esophageal. Not isolated lingual) Coccidioidomycosis Cryptococcosis

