Progressive multifocal leukoencephalopathy (PML), John Cunningham (JC) virus  Fungal  Aspergillosis (invasive disease only)  Blastomycosis  Candidiasis (invasive disease or oropharyngeal, esophageal. Not isolated lingual)  Coccidioidomycosis  Cryptococcosis
Fungal Aspergillosis (invasive disease only) Blastomycosis Candidiasis (invasive disease or oropharyngeal, esophageal. Not isolated lingual) Coccidioidomycosis Cryptococcosis
Aspergillosis (invasive disease only)  Blastomycosis  Candidiasis (invasive disease or oropharyngeal, esophageal. Not isolated lingual)  Coccidioidomycosis  Cryptococcosis
Blastomycosis Candidiasis (invasive disease or oropharyngeal, esophageal. Not isolated lingual) Coccidioidomycosis Cryptococcosis
Candidiasis (invasive disease or oropharyngeal, esophageal. Not isolated lingual)  Coccidioidomycosis  Cryptococcosis
Coccidioidomycosis Cryptococcosis
Cryptococcosis
Histoplasmosis
*
Paracoccidioides infections
Penicilliosis
Pneumocystosis
Sporotrichosis
Other invasive molds: Mucormycosis (zygomycosis) (Rhizopus, Mucor, and Lichtheimia),
Scedosporium/Pseudallescheria boydii, Fusarium
Parasitic
Leishmaniasis (visceral only)
Strongyloidiasis (hyperinfection syndrome or disseminated disease)
Microsporidiosis
Toxoplasmosis
Trypanosoma cruzi infection (Chagas' disease progression) (disseminated disease only)
Cryptosporidiosis (chronic disease only)

Source: Based on Winthrop et al. (2015).

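### Two entries in the Appendix 8 table of opportunistic infections conflict with the study's own modified definition, and criterion 17 and the data-analysis sentence cite the source article without the modifications

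*Protocol*

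**What the plan says.** Protocol Appendix 8 opens with the study definition: "For this study, infections are defined as opportunistic according to a consensus recommendation for clinical and postmarketing settings", followed by a list of modifications. Two of them matter here:

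- On candidiasis: "Candidiasis infections involving only the oral cavity or pharynx are not considered opportunistic". Diagnostic evidence of infection in the esophagus, or further down the gastrointestinal tract, is needed before such a case counts.
- On zoster: "Localized herpes zoster infections are not considered opportunistic". Only multidermatomal or disseminated disease counts.

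The appendix then introduces a table of examples: "These tables are intended to aid the investigator in recognizing infections which may be considered opportunistic". The viral part of that table lists "Herpes zoster (any form" and the fungal part lists "Candidiasis (invasive disease or oropharyngeal, esophageal. Not isolated lingual". Each entry closes its bracket there, with no further qualification. A source note says that the table is based on the consensus article.

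On analysis, the appendix says: "For data analysis, infections will be categorized by Lilly as opportunistic according to the article". That sentence does not repeat the modifications.

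Three other places use the term. Protocol Section 5.2, criterion 17, defines opportunistic by the article and adds a pointer to Appendix 8. Protocol Section 7.1.4 requires withholding for serious or opportunistic infections and takes the definition from Section 5.2. SAP 4.7.4.1 identifies potential opportunistic infections from a preferred-term list, has medical review decide which are confirmed, and refers the reader to the article, to compound-level safety standards and to Appendix 8.

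**The concern.** For two common-sense cases, localized zoster and oropharyngeal-only candidiasis, the definition says no and the table says yes. The table is what a site would have in hand when deciding. The references elsewhere do not settle the matter, because none says that the article applies as modified.

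The classification is used for three things: a required interruption of dosing, an exclusion criterion (Protocol Section 5 does not permit waivers), and a reported safety category. Two sites could handle the same event differently and each point to Appendix 8. It would also be unclear whether continued dosing through such an event is a protocol deviation.

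**Working it through.** No plan figure exists to reproduce, so the check is mainly textual.

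**Definition against table, case by case (Protocol Appendix 8)**

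| Case | Modified definition | Table | Agree? |
|---|---|---|---|
| Localized zoster | Not opportunistic | Listed | No |
| Oropharyngeal-only candidiasis | Not opportunistic | Listed | No |
| Isolated lingual candidiasis | Not opportunistic | Not listed | Yes |
| Esophageal candidiasis | Opportunistic | Listed | Yes |
| Multidermatomal or disseminated zoster | Opportunistic | Listed | Yes |

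The table has 10 bacterial, 8 viral, 11 fungal and 6 parasitic entries: 10 + 8 + 11 + 6 = 35. Two of the 35 conflict with the definition. This counts table lines and says nothing about how often the infections occur.

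**Dosing (Protocol 7.1.4).** For serious or opportunistic infections the hold is required. The row for any acute infection or illness leaves it to the discretion of the investigator and sponsor. The hold itself, once applied, is described the same way in both rows. Serious cases are held on either reading, so the difference is confined to non-serious localized zoster and non-serious oropharyngeal candidiasis: required under the table, discretionary under the definition.

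**Eligibility (Protocol 5.2).** Criterion 16 says: "For at least 30 days before screening and up to the randomization/baseline visit, participants must have no symptoms or signs" of infection, with limited exceptions. Criterion 17 looks back 3 months before screening for serious, opportunistic, chronic (6 weeks or longer) or recurring infections. The interval in which only criterion 17 can decide is:

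- 3 months = 3 × 365.25 / 12 = 91.3 days
- 91.3 − 30 = 61.3 days

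A single oropharyngeal candidiasis episode that was non-serious, lasted under 6 weeks and had cleared by 30 days before screening is excluded under the table and eligible under the definition. Zoster is named separately under recurring infections in criterion 17, so no eligibility effect is claimed for it.

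**Reporting (SAP 4.7.4.1 and SAP Appendix 3).** The preferred-term list contains herpes zoster, oral candidiasis and oropharyngeal candidiasis, so these events reach medical review as potential opportunistic infections. The SAP does not state whether the reviewer applies the article alone or the article as modified, so the confirmed count can differ. All treatment-emergent infections are also tabulated by preferred term, so every event appears somewhere.

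**The case against.** The strongest reply is that the hierarchy is already there. The opening sentence adopts the article with modifications as the study definition, and a modification overrides what it modifies. The table is headed as examples of what may be considered opportunistic and is described as a recognition aid. A broad list for spotting cases can sit beside a narrower definition. Following the table also errs toward withholding drug, which is the cautious direction. In the SAP, a broad search followed by medical review is meant to sort such cases, and the compound-level safety standards, which are not available here, may state the rule.

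Most of this stands. It is why the definition most likely governs and why the effect is small. It does not remove the inconsistency. The definition flatly rules out what the table lists, so permissive wording cannot reconcile them. The neighbouring herpes simplex entry is limited to invasive disease, so an investigator would take the unrestricted zoster entry as deliberate. Criterion 17, on which Section 7.1.4 relies, names the article as the definition and only points to Appendix 8.

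One limit should be kept in view. The article was not available, so what it says on these two infections cannot be checked. The table's source note is only indirect evidence.

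**Conclusion.** The inconsistency is real and minor. Two table entries contradict the adopted definition, and two references (criterion 17 and the data-analysis sentence) omit the modifications. The consequences are those in the working: a required or a discretionary hold for non-serious cases, an eligibility difference for one narrow candidiasis history over about 61 days, and a possible difference in the confirmed opportunistic infection count. The documents give no rate for either infection, so no event count or frequency is claimed.

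A reader might infer that the study has no working definition, that participants would be put at risk by missed holds, or that opportunistic infections would go unreported. The documents support none of these. The opening sentence supplies a definition. The table leans toward withholding, and serious infections are held on any reading. All infections are tabulated by preferred term. PASI 75 is unaffected.

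The conclusion assumes that the sponsor intends the modified definition to apply throughout, which is the natural reading of the opening sentence.

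**What to change.** - In the Appendix 8 table, change the two entries to 'Herpes zoster (multidermatomal or disseminated only)' and 'Candidiasis (invasive, or confirmed in the esophagus or anywhere in the gastrointestinal tract below it; not oral cavity or pharynx alone)'. The candidiasis wording should not be shortened to lower GI, which could be read as leaving out the stomach.
- Add 'with the modifications above' to the data-analysis sentence in Appendix 8.
- Add 'as modified in Appendix 8' to criterion 17. Section 7.1.4 then inherits it.
- In SAP 4.7.4.1, name the modified definition as the criterion for a confirmed opportunistic infection.

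The cost is wording edits that can go into the next protocol amendment, with the usual ethics approval, and one phrase in the SAP. Visits, sample size, data collection and output tables do not change. One consequence should be accepted openly: where criterion 17 is now read as the unmodified article, the edit may slightly narrow the exclusion and the required hold, in line with the definition that the protocol already adopts.
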